9.3.5 Dietary compliance

Dietary adherence will be measured by four days of weighed dietary foods records preferably on four consecutive days together with four days of repeated spot urine collections. Participants in the BCC intervention group will also be instructed to keep a diary on how often their meals deviate from their personal carbohydrate meal plan, how often they adjust their prandial insulin dosage and measure their plasma glucose levels.

Dietary adherence is an important issue and also a measure indicating feasibility of the nutritional education method. Biomarker technologies have been developed for objective assessment of dietary compliance in recent years (37, 38). Several different sugars exist in carbohydrate rich foods and some of them have been shown to be excreted in urine in proportion to intake (39). Intake of several carbohydrate rich foods including total fruit and vegetables (40) and some whole grain foods (41) have been found to result in excretion of marker compounds in urine, while several others are under investigation. The excretion products may therefore be used as additional qualitative biomarkers of carbohydrate rich food intakes.

9.4 Recruitment of participants

SDCC offers courses in BCC and ABC-ACC for all patients with T1D treated in the capital region of Denmark. Patient information regarding the BCC and ABC-ACC courses is available on the SDCC webpage <https://www.sdcc.dk/undersogelse-og-behandling/kurser/Sider/default.aspx>, on info screens and posters and flyers in the waiting areas at SDCC and at each of the diabetes outpatient clinics in the Steno Partner hospitals in the capital region of Denmark (Amager and Hvidovre hospital, Bispebjerg and Frederiksberg hospital, Rigshospitalet, Bornholms hospital and Nordsjællands hospital). In addition, health care professionals (doctors, nurses and dietitians) from SDCC and the Steno Partner hospitals can refer eligible patients treated at their hospital to the courses directly through the electronic medical record (EMR) "Sundhedsplattformen". Information about the courses has been given at meetings and as written materials (handouts and electronic newsletters) to health care professionals at SDCC, and diabetologists and dietitians at each Steno Partner hospital who have been selected to coordinate this initiative and similar initiatives including passing on information about the BCC courses and patient referral procedures to their colleagues.

The BCC and ABC-ACC courses are free of charge and online registration through a link or by e-mailing the course administrator is possible from SDCC's webpage (sdcc.dk). By online registration or email, the patients indicate that they are interested in further contact for the purpose of being signed up for a course.

Subsequently, a course administrator at SDCC will contact all interested or referred patients by telephone to arrange a date for course participation, which is then registered in *Sundhedsplatformen*.

Potential participants for the current study will be recruited among patients signing up for the BCC course, ABC-ACC course or among patients directly referred to the BCC course or ABC-ACC course by their health care professional. As part of the first telephone contact by the course administrator, the patients will be asked if they are interested in further information about a current study regarding courses in carbohydrate counting. In addition, potential eligible participants at the outpatient clinic at SDCC are identified by transferred information from the EMR about diagnosis, diabetes duration, age, sex, insulin treatment modality, HbA1c, previous participation in carbohydrate counting courses, time and number of previous dietitian visits and comorbidities by the primary study investigator. If potentially eligible, the treatment responsible health care personnel will ask the patients at the upcoming visit if they are interested in participation. Subsequently, the responsible care personnel will inform the study investigator about patients interested in participation and the study investigator/personnel will then contact the patient and send the written patient information together with the leaflet "*Forsøgspersoners rettigheder i et sundhedsvidenskabeligt forskningsprojekt*" (appendix 2) by mail or e-mail. Identified patients who do not have an appointment at the clinic in near future, will be contacted by a letter or by a secured e-mail (E-boks) with the written information. Potential study participants will also be recruited through information on sdcc.dk and other electronic media (e.g. sundhed.dk, forsøgsperson.dk, diabetes.dk and social media), patient related networks (e.g. the Danish Diabetes Association) with a short description of the study and contact information for further details. Patients interested in participating in the study will be contacted by phone by the study investigator or study personnel who will offer to send written patient information about the study. If the patients are still interested in participation after having read the written patient information, the study investigator or study personnel who have been delegated the task according to the delegation log, will arrange for a personal meeting to provide oral information about the study (cf. below in section 9.6).

9.5 Study participants

The study will include adult patients with T1D with an initial HbA1c of 53-97 mmol/mol. The following specific inclusion and exclusion criteria are applied.

9.5.1 Inclusion criteria

- Type 1 diabetes
- Age; from ≥ 18 to ≤ 75 years of age
- Diabetes duration; > 12 months
- Multiple daily insulin injection therapy
- Provided voluntary written informed consent

9.5.2 Exclusion criteria

- Practicing carbohydrate counting, as judged by the investigator
- Participated in a BCC group program within the last two years
- Use of insulin pump, or plans of having an insulin pump within the study period
- Fixed dose of rapid acting insulin therapy for meals
- Split-mixed insulin therapy
- Use of an automated bolus calculator
- Gastroparesis
- Pregnancy or breastfeeding, or plans of pregnancy within the study period
- Low daily intake of carbohydrates (defined as below 25 E% or 100 g/day)

- Uncontrolled medical issues, as judged by the investigator or a medical expert
- Concomitant participation in other clinical studies
- Unable to understand the informed consent and the study procedures

9.5.3 Criteria for withdrawal

One or more of these criteria will result in withdrawal of the participant from the study:

- Participant withdraws the informed consent
- Pregnancy or other safety concerns, as judged by the investigator
- Participant's general condition contraindicates continuing the study, as judged by the investigator or a medical expert
- Non-compliance with the study protocol or lack of corporation as judged by the investigator
- Lost to follow-up
- Other reasons determined by the investigator

Participation in the study is voluntary, and participants have the right to withdraw from the study without providing a reason and with no loss of benefits to which the participant is entitled. If a participant chose to withdraw the study personnel and investigator must be informed immediately, and every effort should be made to complete the early termination assessments and document the reason for discontinuation. For participants considered lost to follow-up, the last completed visit will be recorded. The investigator has the right to terminate participation of any participant at any time if they deem it in the participant's best interest. Study participants will not be excluded from the study if they do not attend all visits.

Participants who withdraw from the study will not be replaced. Follow-up will be performed for withdrawn participants at the end of the study and used in analyses if allowed by the participant.

9.6 Participant information

Written, informed consent will be obtained from all participants prior to entry into the study. The study investigator /study personnel will contact all interested patients by phone and provide information about the study. If the patient is interested in participating in the study, the study investigator/study personnel will send the written patient information (appendix 1) and the leaflet "*Forsøgspersoners rettigheder i et sundhedsvidenskabeligt forskningsprojekt*" (appendix 2) by mail or e-mail. If the patient is still interested in study participation after having read the written patient information, the study investigator /study personnel will schedule a personal meeting with the patient, offering the possibility of bringing a confidant. At the personal meeting the study objectives, significance, content and requirements including risks and implications of the study and principles for randomization with allocation to either one of two interventions or a control group will be orally explained.

In particular the patient will be informed about the following:

- The possibility of withdrawing from the study at any time without losing any patient-related benefits
- How personal and health-related data will be collected and used during the study
- That all personal and health-related data will be anonymized

The patient will be given time to discuss any questions and will be informed that he/she has at least 24 hours to decide on participation in the study. If the patient decides to participate in the study right away, the patient and the study investigator/study personnel will sign the written informed consent, and the investigator/study personnel will perform a screening to assess if the patient is eligible for inclusion in the study (see section 9.7 for screening procedure). Patient eligible for inclusion in the study will be booked for

a visit (V1) where the baseline measurements and randomization will be carried out by the study investigator/study personnel. If the patient needs more time to decide if he/she wants to participate in the study, the study personnel will contact the patient again within the next week. If the patient decides to participate in the study after having had time for reflection, the patient will be invited to a first visit (V1) with the purpose of screening for study eligibility, collection of baseline measurements and randomization. The patients are informed that written informed consent will be obtained prior to commencement of any study related procedures.

9.7 Screening procedure and informed consent

The study investigator/study personnel must receive a written signed consent (see appendix 4) from the patient before performing a screening. The signed consent form must also be signed by the investigator or study personnel who have been delegated the task according to the delegation log, and a copy of the signed consent must be handed over to the participant together with a copy of the patient information sheet before performing the screening. The original written signed consent will be retained by the study investigator.

In addition, the patient will be asked to sign an independent written signed consent for donation of biologic material to a biobank for future research (see appendix 5). Rejection of donation of samples to the biobank, will not affect participation in the study.

The investigator/study personnel will perform a screening to assess if the patient is eligible for inclusion in the study based on the inclusion and exclusion criteria listed in section 9.5.1 and 9.5.2. This includes having a non-fasting blood sample collected for assessment of HbA1c. The sample will be analysed instantly, and the result will be available in the patient's EMR *Sundhedsplatformen* within 5-10 min for the investigator/study personnel to assess.

The screening also includes a personal interview with the patient according to a study specific standard operational procedure (SOP) to assess the patient's type of diabetes, place of treatment in the capital region of Denmark, age, diabetes duration, insulin treatment regime, use of insulin pump, use of continuous glucose monitoring (CGM), use of a Freestyle Libre, previous participation in a carbohydrate counting course, existing carbohydrate counting practices including use of an automated bolus calculator, gastroparesis, daily intake of carbohydrates, current pregnancy or plans of pregnancy, breastfeeding, uncontrolled medical issues or concomitant participation in other clinical studies and language skills in Danish.

If a participant is not eligible for inclusion in the study the cause of screening failure will be recorded, and the patient will be offered participation in on a BCC course or ABC-ACC course as a patient instead of as a study participant.

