10.8 Electronic medical record data

The following data from the participants' EMR *Sundhedsplatformen* will be collected at V1 by the investigator. Changes in glucose- and cholesterol-lowering medications and changes in other medications e.g. diuretics throughout the study will be registered after visits V5 and V6 and total number of visits at a diabetologist and diabetes nurse during the study period will be registered at V6.

- Type of diabetes
- Gender
- Date of birth
- Smoking status
- Diabetes duration
- Gastroparesis
- Prescribed insulin, types and dosages
- Prescribed oral antidiabetics, types and dosages
- Prescribed cholesterol lowering medication, types and dosages
- Prescribed other medication and dose or changes in dose of other medication
- Previous participation in a BCC group program
- Use of open CGM
- Use of a Freestyle Libre
- Use of an automated bolus calculator

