13.2 Statistical methods

Intention-to-treat (ITT) analysis will be performed as the primary analysis on all primary and secondary outcomes after the last participant has participated in the last visit. Missing values will be handled with a last observation carried forward approach for ITT analysis. Per-protocol (PP) analysis will only be performed in case of sensitivity testing.

Parametric tests (general linear models) will be used to test differences in outcomes from baseline to follow-up. Heterogeneity in responsiveness to the interventions will be tested by dividing each intervention group into smaller groups based on data distribution (medians) or clinically meaningful cut-points. If model assumptions cannot be met even after logarithmic transformation, non-parametric tests will be used. Plots of residuals versus predicted values will be used to judge normality. Metabolic patterns will be tested with multivariate statistics. Adjustment for relevant confounders will be performed. Two-sided tests will be used. *P* values of <0.05 are considered significant. The statistical programs SPSS and SAS will be used for data analysis.

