13.3 Determination of sample size

Allowing for drop-outs (~20%) and subgroup analyses we plan to include a total of 231 patients in our study. This is based on sample size calculations which suggested that including 64 participants in each of the study groups would give us 80% power to detect a clinically meaningful difference in change in HbA1c of 3.5 mmol/mol between the BCC group versus the control group or the ABC-ACC group versus the control group with a 5% significance level using a two-sided test and an estimated standard deviation (SD) of 7 mmol/mol. This SD has previously been used for sample size calculations in ACC trials (28) and was similar to what we found in our evaluation of our BCC courses on mean changes and SD of HbA1c after 6 months in completers with T1D (n=185). MAGE has only been used as an outcome measure of glucose variability in a few randomized controlled dietary intervention studies of patients with diabetes (42, 43) showing differences in changes in MAGE up to 4.8 mmol/l (SD: 1.0) after a 12-week carbohydrate counting intervention (42). By including 77 participants in each study group we will have a power of 80% (alpha level of 0.05) in a two-sided test to detect a clinically meaningful difference in the change in MAGE during the intervention period (week 24) of ≥ 0.35 mmol/l (SD 0.7 mmol/l) between the study groups as presented in **Table 5**.

Table 5: Sample size calculations

Difference in HbA1c, mmol/mol (SD 7.0)	Difference in MAGE, mmol/l (SD 0.7)	Net total no of participants in the study (BCC group vs control or ABC-ACC group vs control)	No of participants given a dropout rate of 20%
2.0	0.20	582	698
3.0	0.30	261	315
3.5	0.35	192	230
4.0	0.40	150	180

14 Data management

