### Baseline participant characteristics

The distribution of all continuous outcomes included in baseline characteristics will be visually inspected using QQ-plots and histograms; those with a Gaussian distribution will be presented as means and standard deviations and those with a non-Gaussian distribution will be presented as medians plus 25th and 75th percentiles, number of observations will be presented for each outcome presented. Categorical data will be summarised by numbers and percentages. Tests of statistical significance will not be undertaken for baseline

characteristics according to the CONSORT Statement for reporting clinical trials; rather the clinical importance of any imbalance will be noted (18).

The following outcomes will be included in the baseline participant characteristics table for all participants combined and stratified by randomisation group:

- Number of participants, n
- Age (years)
- Gender, male, n and %
- Ethnicity, white, n and %
- Smoking status
  - Current smoker, n and %
  - Number of smoking years
- Education
  - Elementary school, n and %
  - Upper secondary education, n and %
  - Vocational, n and %
  - Short further (< 3 y), n and %
  - Medium further (3-4 y), n and %
  - Long further (> 4 y), n and %
- Family status
  - Living alone with or without children at home, n and %
  - Living with a partner with or without children at home, n and %
- Diabetes duration (years)
- HbA1c (mmol/mol)
- Blinded sensor data
  - MAGE (mmol/l)
  - Mean plasma glucose, mmol/l
  - Time in range (TIR): % of readings and time 3.9-10.0 mmol/l
  - Time above range (TAR): % and readings and time 10.1-13.9 mmol/l
  - Time below range (TBR): % readings and time 3.0-3.8 mmol/l
  - Glycaemic variability, coefficient of variation (CV), %
  - Glycaemic variability, standard deviation (SD), mmol/l
- Body weight (kg)
- BMI, kg/m^2
- Waist/Hip ratio, unitless (women)
- Waist/Hip ratio, unitless (men)
- Systolic blood pressure (mmHg)
- Diastolic blood pressure (mmHg)
- LDL cholesterol (mmol/l)
- Glucose-lowering medication
  - Basal insulin dose, units/day
  - Prandial insulin dose, units/day
  - GLP-1, n and %
- Antihypertensives, n and %
- Lipid-lowering medication, n and %
- Use of flash or continuous glucose monitors, n and %

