## Analysis methods

Analyses of the primary outcomes will be performed based on efficacy estimates.

Before further analysis and before unblinding, all variables will be inspected to detect outliers to uncover potential errors, such as registration errors.

All continuous outcomes covered by this SAP will as a rule be modelled using baseline corrected repeated measures regression (22) with the following fixed effects and interactions between fixed effects: Visit, Visit (factorial)\*Treatment. Data from V1, V2, and V3 will be included in the analysis. The models will be specified with a restricted maximum likelihood estimation method and a repeat on participant level (unstructured covariance structure). Model fit will be evaluated using graphical methods before estimating the treatment effects and if necessary, outcomes will be log-transformed. Estimated mean differences (CI95%) between groups (CI95%), conditional means (CI95%), and within group changes (CI95%) will be extracted from the model. For log-transformed outcomes the results will be back-transformed and be presented as the ratio between estimated mean differences (CI95%), estimated conditional geometric means (CI95%) and relative changes within groups (CI95%), respectively. If log-transformation cannot meet distribution assumptions, a generalized mixed linear model with an appropriate distribution will be applied instead of the repeated measures regression model. In case the distribution does not comply with the distributions available in the generalized mixed linear model a non-parametric test will be used to compare the change scores for the given outcome.

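### Personal CGM or flash use is collected before randomisation but is not a covariate in the primary models: a modest, nearly free gain in precision, with later device starts a separate matter to describe by arm

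*Protocol*

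**What the plan says.** **Collection.** Protocol section 9.7 lists among the screening interview items "use of continuous glucose monitoring (CGM), use of a Freestyle Libre". Section 10.8 takes open CGM and Freestyle Libre use from the medical record at V1.

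**Design.** Section 9.5.2 excludes insulin pumps and automated bolus calculators but not personal glucose sensors. Protocol section 9.8 and the SAP's Randomisation section stratify on sex and HbA1c only.

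**Analysis.** The SAP's Analysis methods section specifies a baseline-corrected repeated measures model "with the following fixed effects and interactions between fixed effects: Visit", followed by the visit-by-treatment interaction. It contains no other term. Protocol section 13.2 says "Adjustment for relevant confounders will be performed" and names no variable. The SAP plans no additional analyses.

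**Description.** The SAP's baseline table includes "Use of flash or continuous glucose monitors, n and" per cent, overall and by arm, and the SAP undertakes to comment on whether an imbalance matters clinically.

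**After V1.** Section 10.8 states: "Changes in glucose- and cholesterol-lowering medications and changes in other medications e.g. diuretics throughout the study will be registered after visits V5 and V6". Visit counts are added at V6. Neither this section nor the SAP's list of other outcomes includes a change in personal sensor use.

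**The concern.** Someone who sees their own glucose continuously may respond differently to dietary education from someone who does not. If so, device use predicts the change in HbA1c and MAGE beyond the V1 value. Leaving it out of the model keeps that variation in the residual, although the trial already holds the variable. The general promise of adjustment in the Protocol becomes no covariate at all in the SAP. If the baseline table shows an imbalance, the plan offers only a comment or an adjustment chosen after the data are seen.

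A second issue is of a different kind. Regular diabetes care continues for 48 weeks and allocation is known. If participants in one arm take up sensors more often than those in another, the contrast mixes the effect of education with that of the device. Nothing in the documents would let a reader see this.

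**Working it through.** **Plan's own figure.** Inputs from Protocol section 13.3: "clinically meaningful difference in change in HbA1c of 3.5 mmol/mol"; "with a 5% significance level using a two-sided test and an estimated standard deviation (SD) of 7 mmol/mol"; "including 64 participants in each of the study groups would give us 80% power". The standardised effect is 3.5/7 = 0.5. A two-sample t-test at two-sided 5% and 80% power needs 63.77, so 64 per arm, and 3 × 64 = 192, as in Table 5. Power at 64 per arm is 80.1%. For MAGE, 0.35/0.7 = 0.5, so every figure below applies to MAGE at the same share of variance explained.

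**Baseline covariate.** Let p be the share of users and b the difference in week-24 HbA1c change between users and non-users that remains after baseline correction. The documents give neither, so both are assumed: p from 0.2 to 0.5, b from 0 to 5 mmol/mol.

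R² = p(1 − p)b²/SD², and the residual SD is 7 × √(1 − R²).

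| p | b (mmol/mol) | R² | Power, 64 per arm | n per arm for 80% |
|---|---|---|---|---|
| any | 0 | 0% | 80.1% | 64 |
| 0.2 | 1 | 0.16 × 1/49 = 0.3% | 80.3% | 64 |
| 0.2 | 2 | 0.16 × 4/49 = 1.3% | 80.7% | 63 |
| 0.3 | 3.5 | 0.21 × 12.25/49 = 5.3% | 82.2% | 61 |
| 0.5 | 5 | 0.25 × 25/49 = 12.8% | 85.2% | 56 |

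This is power for the significance test alone. It does not cover the further condition in SAP Section 2 that the estimate reach the minimal important difference. The calculation treats SD 7 as the residual SD before the device term is added.

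**Chance imbalance is the same variation.** With p = 0.3, the 95% range of the difference in user share between two arms is 1.96 × √(2 × 0.21/64) = ±0.159. With b = 3.5 this moves the contrast by ±0.56 mmol/mol. The unadjusted 95% half-width is 1.96 × 7 × √(2/64) = 2.43. The squared ratio, (0.56/2.43)², is about 0.053, which is the R² in the table. The imbalance is therefore already inside the confidence interval and is not an extra harm.

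**Starts after V1.** These need a separate calculation. Suppose the proportion starting a device is δ higher among controls than in an intervention arm, and b = 3.5 (again assumed):

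- δ = 0.10: the contrast shrinks by 0.10 × 3.5 = 0.35 to 3.15, and power is 71%.
- δ = 0.20: it shrinks by 0.20 × 3.5 = 0.70 to 2.80, and power is 61%.

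The reverse pattern inflates the contrast by the same amounts. A baseline covariate changes none of this.

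**The case against.** The case for leaving the model alone is strong in several respects.

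- **The effect is assumed.** An established user's V1 HbA1c and MAGE already reflect the device, and the model corrects for V1. Only an effect on later change is left. Values of b near 0 are plausible, and there the gain is negligible. The upper end, 5 mmol/mol, exceeds the trial's own minimal important difference. This stands, and it is why the range starts at zero.
- **Other variables could be named too.** Age, diabetes duration or education would support the same argument, and adding device use while omitting sex, a stratification factor, would be arbitrary. This also stands, so sex belongs in the model as well.
- **There is some handling already.** Baseline use is tabulated by arm. That shows an imbalance but does not say what would be done about it.

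A reader might also infer more than the documents support:

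- *Bias or a raised type I error from omitting the term.* Allocation is random, so omitting a baseline covariate does neither.
- *An underpowered trial.* SD 7 is a planning value with no device variation removed, and 64 per arm reproduces.
- *The Protocol itself treats sensor use as a driver of benefit.* Sections 6.1 and 7.1 concern plasma glucose monitoring and do not mention personal CGM. At most they suggest effect modification, which a main effect with its visit interaction does not test.
- *A contradiction in calling the study sensor data blinded.* The label describes the study sensor's output and makes no claim about participants' own devices.
- *The SAP dropped a specified device adjustment.* Section 13.2 named no variable.

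**Conclusion.** The point holds as a modest precision improvement. A baseline variable that the trial already holds could be prespecified at almost no cost, and doing so would give content to the Protocol's unspecified promise of adjustment. Under the assumed 20-50% users and 0-5 mmol/mol residual difference, the gain runs from nothing to about 5 percentage points of power (80.1% to 85.2%), equivalent to 0 to 8 participants per arm (64 − 56). The same holds for MAGE at equal R². No result would be invalid without it.

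Device changes after V1 are a separate issue. They are post-randomisation events, so they are neither a baseline prognostic factor nor a valid covariate. Unequal uptake could shift the contrast in either direction. The documents give no evidence that it occurred, and the figures of 71% and 61% only illustrate assumed differences. The defect is that the plan provides no way to describe it.

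**What to change.** 1. **SAP Section 6, before analysis.** Add personal CGM or flash use (yes/no) and sex, each with its interaction with visit, as fixed effects in the HbA1c and MAGE models. Take device use from the screening interview. The SAP places randomisation at the end of the screening visit, so the V1 record extract may fall after allocation. The SAP puts the analysis after its own upload, so prespecification is still possible on its terms. The cost is two terms and their interactions, from data already collected.

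2. **Device changes after V1.** Where the medical record allows, extract starts and stops of a personal CGM or flash device in the medication review covering V5 and V6 (V2 and V3 in the SAP's numbering). Tabulate them by arm, as description only. The SAP describes randomisation in the past tense, so this is probably a retrospective search of up to 231 records, and its completeness should be reported. It costs more than the covariate, but it changes no eligibility rule, visit or treatment.
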